5.13 Safety Analyses

The safety endpoints in this study include adverse events, device complications, and the Beck Depression Inventory (BDI). Other assessments, including Neurological Examinations, and Physical Examinations will be summarized.

Safety analyses will be based on the ITT population.

The safety results will be reported overall and for each of the following study phase:

- study entry through surgery
- through treatment to visit 5

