2.1 Primary Objective

The primary objectives of this study are to assess:

- the efficacy of VNS therapy compared to standard rehabilitation (active control includes the surgical intervention and sham stimulation) in the recovery of upper limb motor function after stroke.
- safety of the surgical intervention and VNS stimulation

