3 STUDY DESIGN

This protocol is a pivotal study of up to 120 subjects and 15 clinical sites. All subjects are implanted with the Vivistim System[®] and then randomized to either study treatment or active-control treatment. Study treatment is vagus nerve stimulation (VNS) delivered during rehabilitation. Active control treatment is rehabilitation (standard-of-care treatment) with only a minimal amount of VNS at the start of each session intended to support blinding.

This study has three distinct stages:

Stage I – blinded, with consent, assessment, implant, baseline assessment, acute therapy (6 weeks), and follow-up assessment periods (Days 1, 30 and 90 post-acute therapy)

Stage II – unblinded follow-up, including additional therapy sessions and quarterly assessments through one year post implant. Control group subjects crossover to VNS treatment.

Stage III - annual (yearly) follow-up through commercial approval to allow the device to remain implanted and the subject to continue at-home use. Additional rehabilitation sessions are allowed at the investigator's discretion.

This statistical analysis plan (SAP) is focused on Stage I (blinded, randomized portion). A future SAP will focus on Stage II and Stage III, and will be developed prior to the first subject completing Stage II (first subject reaching one-year post implant).

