4 ANALYSIS SETS & SCHEDULE

4.1 Intent to Treat (ITT)

The ITT population will include any subject who is randomized, and will be the basis of the efficacy and safety analyses. All subjects who undergo surgery will be included in the safety population, with all adverse event and safety information reported.

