5.10 Demographic and Baseline Characteristics

Demographic and Baseline characteristics will be presented for all subjects and for each analysis population as total enrolled and by treatment group. Gender, race, and ethnicity will be summarized by count and percentage. Age, height, body weight, and BMI, will be presented with numeric descriptive statistics.

The subject's age is calculated as the number of years from the subject's date of birth to the date the Informed Consent signed:

$$\text{Age} = [\text{Date Informed Consent Signed} - \text{Date of Birth}] / 365.25$$

Demographic and Baseline Characteristics will be summarized for the ITT, PP, and Safety populations, should these populations be different. All subjects who undergo surgery will be included in the safety population, with all adverse event and safety information reported.

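### The SAP names two different safety analysis sets; the one chosen in 5.13 (randomised subjects) would leave anyone operated on but not randomised out of the surgical event rates.

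*SAP*

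**What the plan says.** Two statements in the SAP put safety on the randomised set. Section 5.13: "Safety analyses will be based on the ITT population". The first sentence of section 4.1: "The ITT population will include any subject who is randomized, and will be the basis of the efficacy and safety analyses".

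Other statements point to a different set. The second sentence of 4.1 reads: "All subjects who undergo surgery will be included in the safety population, with all adverse event and safety information reported". Section 5.10 repeats that sentence and says baseline characteristics will be "summarized for the ITT, PP, and Safety populations, should these populations be different", so the SAP itself foresees that the sets may not coincide. Section 5.5 adds that all data collected are included in the assessment of safety.

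On the order of events, section 3 says: "All subjects are implanted with the Vivistim System[®] and then randomized". Section 3.1 puts randomisation on the day of implant surgery.

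On purpose, section 2.1 lists among the primary objectives "safety of the surgical intervention and VNS stimulation". Section 5.13 has a reporting phase that runs from study entry to surgery. Sections 5.13.1 and 5.13.2 summarise adverse events and device complications by treatment group.

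**The concern.** The set named in the operative safety section is not the set that the SAP defined for safety. A programmer following 5.13 would build the safety tables on ITT. One following the second sentence of 4.1 would build them on all operated subjects. Both would be following the plan.

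The difference matters because, in the stated order, surgery comes before entry to the ITT set. A subject whose implantation is abandoned, or who has an intra-operative event that prevents allocation, has been exposed to the surgery but is not randomised. Such a subject is outside ITT because something went wrong at surgery, so the omission would not be random and could only lower the tabulated surgical complication rate. Section 1 says these results are meant to support a filing for market approval, and surgical safety is one of the two primary objectives. If the conflict stays, the choice of set could also be made after the events are known.

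**Working it through.** **The plan's own safety figure.** Section 3.4 gives a 95% probability of seeing at least one occurrence of an event with a true rate of 3% in 100 subjects. The check is 1 − (1 − 0.03)^100 = 1 − 0.97^100 = 0.952. The figure reproduces and is not in dispute.

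**The statements side by side.**

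| SAP section | Set for safety | Operated but not randomised |
|---|---|---|
| 4.1, first sentence | ITT (randomised) | excluded |
| 5.13 | ITT (randomised) | excluded |
| 4.1, second sentence | all who undergo surgery | included, events reported |
| 5.10 | all who undergo surgery; may differ from ITT | included, events reported |
| 5.5 | all data collected | included |
| 5.13.1, 5.13.2 (tables) | by treatment group | no column |

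The first two rows cannot hold together with the next three for a subject who is operated on but not randomised. Under the order in section 3, such a subject is possible.

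**Size of the effect.** Let N be the number operated on, u the number of these not randomised because of a surgical complication, and k the number of randomised subjects with a complication.

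- Rate on ITT = k / (N − u)
- Rate over all operated = (k + u) / N

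N = 120 is the cap on implants in sections 3 and 3.4. The SAP gives neither u nor k, so both are assumed here.

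| k | u | ITT | All operated |
|---|---|---|---|
| 2 | 0 | 2/120 = 1.7% | 2/120 = 1.7% |
| 2 | 1 | 2/119 = 1.7% | 3/120 = 2.5% |
| 2 | 2 | 2/118 = 1.7% | 4/120 = 3.3% |
| 3 | 1 | 3/119 = 2.5% | 4/120 = 3.3% |
| 3 | 5 | 3/115 = 2.6% | 8/120 = 6.7% |

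With k = 2, one omitted subject understates the rate by about a third (1 − 1.68/2.50 = 0.33), and two omitted subjects by about half (1 − 1.69/3.33 = 0.49). The proportion depends heavily on the small assumed k. With k = 3 and u = 1 it is about a quarter (1 − 2.52/3.33 = 0.24). With u = 0 the two sets give the same rate.

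**The case against.** The best defence is that nothing is lost from the report. Sections 4.1 and 5.10 commit to reporting all adverse event and safety information for everyone operated on, section 5.5 includes all collected data, and section 5.13.1 provides listings. That stands. A reader might infer from 5.13 that a complication preventing randomisation disappears from the trial's safety reporting, or that the safety population serves only the baseline tables. The documents do not support either reading. What is lost is the subject's place in the rates and in the tables by treatment group.

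A second defence is that same-day randomisation leaves a short window. Only an event before allocation on that day could keep an operated subject out of ITT, and later complications are counted. This also stands, and it makes the affected group probably small. Section 3.1 does not say at what point in the day allocation happens; the order rests on the design statement in section 3. A reader might therefore infer that the surgical rates will be biased downward. The documents show only that they would be if such a subject occurs.

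Third, section 5.4 specifies hypothesis tests for efficacy only, so no safety test changes. That is correct, but the tabulated rates are themselves the evidence on the safety objective.

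None of this resolves the conflict between 5.13 and the second sentence of 4.1, or gives an unrandomised subject a column.

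**Conclusion.** The SAP contradicts itself on the safety analysis set and should be corrected before database lock. The contradiction is certain from the text. Its numerical effect is not, because it depends on how many subjects are operated on but not randomised, and the SAP gives no such number. If there are none, the effect is nil. If there is one, and surgery going wrong is the reason, the surgical complication rate is understated on a primary objective: about 1.7% instead of 2.5% in the example with two further events and 120 operated subjects. This rests on implantation preceding allocation, as section 3 states, and on the assumed event counts.

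A reader might also expect the ITT denominator to be inflated by subjects randomised but never operated on. Under the order in section 3 that should not happen, so it is not part of the finding.

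**What to change.** 1. In 5.13, state that the safety analyses are based on the Safety population, meaning all subjects who undergo surgery.
2. In the first sentence of 4.1, delete the words 'and safety', so that ITT is the basis for efficacy only.
3. Report surgery-related and device-related events over all operated subjects as one total, beside the treatment-group columns, and show any subject operated on but not randomised in a separate column.

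The cost is two wording changes and one additional column or total in the safety tables. No further data are needed, since the SAP already commits to reporting events for everyone operated on. The reported surgical event rate may become slightly less favourable.

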3.3 Study Schedule and Treatment

Stage I: Subjects will be screened and assessed for upper limb paresis associated with stroke using a detailed stroke history evaluation (including type, location, onset, neurological evaluation, etc.) and various assessment scores to determine the level of disability in performing everyday tasks. Clinical evaluations by a stroke expert will confirm subjects entering the study exhibit a moderate to severe motor impairment in the upper extremity (UE) (as indicated by a FMA-UE score of 20 to 50) and have at least a nine-month history of the disorder. After informed consent signature, repeat assessments and other measurements will be recorded prior to randomization. Subjects will maintain their group assignments through Visit 7 (end of Stage I, assessment follow-up).

Subjects will start study therapy after an approximately one-week recovery period after surgery. This time period may vary depending on schedules and subject recovery times. The assessments after surgery, and before treatment (Visit 4) will be the baseline for statistical analyses. After a 6 week acute treatment period, post treatment assessments will be done at Visit 5 (1 Day post treatment), Visit 6 (30 Days post treatment), and Visit 7 (90 Days post treatment). During this 90 day post treatment period, subjects will not receive in-clinic rehabilitation, but are given a magnet to swipe just prior to performing their in-home rehabilitation for 30 minutes daily. The magnet activates VNS in the VNS group subjects but does not activate VNS in the Control subjects.

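### The by-phase safety summaries stop at Visit 5, so the Visit 5 to Visit 7 home-stimulation period has no phase, and the second phase has no stated start

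*SAP*

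**What the plan says.** SAP 5.13 sets the reporting rule: "The safety results will be reported overall and for each of the following study phase". Two phases follow: "study entry through surgery" and "through treatment to visit 5". No phase after Visit 5 is listed, and the second entry gives an end but no start.

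Section 3 fixes the scope: "This statistical analysis plan (SAP) is focused on Stage I (blinded, randomized portion"). It describes Stage I as including "follow-up assessment periods (Days 1, 30 and 90 post-acute therapy"), which are Visits 5, 6 and 7. Stage II starts after Visit 7 and is left to a separate plan (3, 5.14).

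On the time between surgery and therapy, 3.3 says: "Subjects will start study therapy after an approximately one-week recovery period after surgery". On the 90 days after therapy, when subjects exercise at home for 30 minutes daily and swipe a magnet first, 3.3 says: "The magnet activates VNS in the VNS group subjects but does not activate VNS in the Control subjects".

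Section 2.1 names as a primary objective the "safety of the surgical intervention and VNS stimulation".

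**The concern.** The SAP chose to report safety by phase, but its list ends before the stage it covers. The stretch left out is one in which the arms differ clearly. In clinic, control subjects also receive the first four stimulations of every session (3.2). At home their magnet delivers none, while the VNS arm is stimulated. It is also the part of Stage I in which subjects trigger stimulation themselves.

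As the plan stands, a reader of the phase tables would see no by-arm incidence of adverse events, serious adverse events or device complications for home use. The second phase has a separate weakness. Two programmers could start it on different days, one after surgery and one at the first therapy session, and produce different tables from the same data.

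**Working it through.** **1. The SAP's own safety figures (3.4).** These are not in dispute and they reproduce.
- Chance of at least one event at a 3% rate in 100 subjects: 1 − 0.97^100 = 0.952, against the stated 95%.
- Exposure: 100 × 42 days = 4200 subject-days = 600 weeks = 4200/365.25 = 11.5 years, as stated. This counts the six weeks of therapy only.

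**2. Length of the period with no phase.** Visit 5 is Day 1 and Visit 7 is Day 90 after therapy (3.3), so the gap is 90 − 1 = 89 days per subject.
- Relative to therapy: 89/42 = 2.1 times as long.
- In subject-days: 100 × 89 = 8,900 in total, of which 50 × 89 = 4,450 in a VNS arm of 50.

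**3. Share of post-implant Stage I.** Post-implant Stage I lasts r + 42 + 90 days, where r is the recovery time. The SAP gives about 7 days and says it may vary; 14 days is an assumed upper case.

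| r (days) | Post-implant Stage I | Share after Visit 5 |
|---|---|---|
| 7 | 139 | 89/139 = 64% |
| 14 | 146 | 89/146 = 61% |

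**4. The second phase under its two readings.**
- If it starts straight after surgery, it lasts r + 42 + 1 days. Recovery takes up 7/50 = 14% of it, or 14/57 = 25% with r = 14.
- If it starts at the first therapy session, it contains no recovery time, but the recovery period then has no phase either.

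The text does not decide between them.

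**5. Whether the missing table can be recovered by subtraction.** Let A, B and C be the sets of subjects with an event in phase 1, in phase 2 and after Visit 5. The overall count is |A ∪ B ∪ C|, so

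|C| = |A ∪ B ∪ C| − |A ∪ B| + |C ∩ (A ∪ B)|.

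The phase tables give |A| and |B|. They give neither |A ∪ B| nor the number of subjects with events both before and after Visit 5. Incidence for the home period therefore cannot be derived from the planned tables. It would have to be rebuilt from the listings.

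**6. Interaction with the date rule.** SAP 5.5 sets missing or incomplete adverse event start dates to the implant date. An undated event from therapy or home use is thus moved to the surgery boundary. Adding phases without addressing this would carry the problem into the new tables.

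**The case against.** The strongest reply is that no safety information is lost. Events between Visit 5 and Visit 7 enter the overall results and the listings. SAP 5.13.1 tabulates adverse events by treatment group and summarizes them by relatedness to device and to surgery. The Beck Depression Inventory is compared from Visit 4 to each later evaluation (5.13.3), and examinations are summarized by scheduled time point (5.13.4, 5.13.5). All of this stands, and it limits the point to by-period summaries of adverse events and device complications. It does not close the gap: relatedness is a judgement about cause and does not give time of onset, and the overall total mixes surgical, clinic and home events.

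A reader might infer more than the SAP supports in four ways:

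- **That stimulation safety cannot be separated from surgical safety.** Both arms are implanted and randomized 1:1, so the between-arm comparison reflects the difference in stimulation. The relatedness summaries also distinguish device from surgery.
- **That surgical events dilute the comparison.** Events arising equally in both arms add noise but do not bias an absolute difference, and no formal test of adverse events is planned.
- **That about two-thirds of post-implant events fall in no phase.** This needs a constant event rate from the day of surgery, which nothing in the SAP supports. The shares above are shares of time. They are not shares of stimulation dose either, since the SAP does not state how long in-clinic sessions last.
- **That the second phase definitely merges recovery with therapy.** That is one reading of a phase whose start is not given.

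**Conclusion.** The point holds as a gap in reporting by time of onset. The named phases omit Visit 5 to Visit 7, about 89 days per subject and roughly 61–64% of post-implant Stage I time. That range rests on nominal visit days and on recovery of 7 to 14 days, where 14 is an assumption. In this period only the VNS arm's magnet delivers stimulation, and the safety of stimulation is part of a primary objective. The second phase has no stated start, so recovery may or may not be combined with therapy.

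The overall by-arm and relatedness summaries are unaffected, and so are the efficacy analyses. This is a worthwhile, low-cost improvement to the safety tables; it does not undermine the safety evaluation.

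**What to change.** In SAP 5.13:

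1. Add a phase from Visit 5 to Visit 7.
2. State the start and end of every phase, including which phase the day of surgery belongs to. One workable layout is study entry through surgery, surgery to first therapy session, first session to Visit 5, and Visit 5 to Visit 7. Other layouts would do if the boundaries are explicit.
3. Report the incidence of adverse events, serious adverse events and device complications by arm for each phase.
4. Show events whose start date was imputed under 5.5 separately in the by-phase tables, so that they are not silently assigned to the surgery boundary.

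The cost is SAP wording and additional table columns. No further follow-up is needed, because the final Stage I analysis already waits until the last subject completes Stage I (5.6). It is assumed that surgery, first-session and visit dates are in the database; the SAP does not say so directly.

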5.13.1 Adverse Events

Adverse Events (AEs) are defined as any undesirable medical occurrence in a study participant, whether or not considered related to the study devices or procedure, which is identified or worsens during the clinical study.

Serious Adverse Events (SAEs) are defined as adverse events that result in death, are life threatening, require inpatient hospitalization greater than 24 hours, or prolongation of an existing hospitalization, require intervention to prevent permanent impairment/damage, or result in persistent or significant disability/incapacity.

Serious Unanticipated Adverse Device Events (SUADEs) are defined as serious adverse experiences directly related to the use of the investigational device leading to injury, illness, or death of a study participant not previously identified in nature, severity or degree of incidence in the protocol.

Adverse Events will be reported by the investigator and will be tabulated by treatment group. Summaries by relatedness to device and surgery, as well as severity, will be provided. SAE and SUADEs will also be summarized by treatment group.

Listings of AE, SAE, and SUADE data will be provided to supplement the tabulated results.

5.13.2 Device Complications

Device complications will be listed by subject and summarized by treatment group.

5.13.3 Beck Depression Inventory

The change in the Beck Depression Inventory score from Visit 4 will be compared to each subsequent evaluation to determine any change in depression category, and as a change in total score. The proportion of subjects with worsening depression will be summarized for each treatment group.

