4.4 Schedule

The table below indicates the primary, secondary, and other analysis timepoints and measures. The change between each visit and the pre-therapy baseline (V4) is the measure of interest, and the difference between the two treatment groups will be analyzed. Within-group changes will also be analyzed.

	Visit 5 (One day after 6-weeks of therapy)	Visit 7 (90 days after 6-weeks of therapy)	Long-Term (6,9,12m after 6-weeks of VNS) Or (LT4, LT5, LT6)	Crossover (Control one day after 6-weeks of VNS [LT1] compared to V7 (prior to start of VNS))
	UEFM Change (primary)	UEFM Response (2 nd)	UEFM Change (o)	UEFM Change (o)
	UEFM Response (o)	UEFM Change (2 nd)	UEFM Response (o)	UEFM Response (o)
	WMFT (o)	WMFT (2 nd)	WMFT (o)	WMFT (o)
	QOL (o)	QOL (o)	QOL (o)	QOL (o)
	BDI (o)	BDI (o)	BDI (o)	BDI (o)
	MAL (o)	MAL (o)	MAL (o)	MAL (o)

o = other (not a primary or secondary analysis)

UEFM – Upper Extremity Fugl-Meyer; WMFT – Wolf Motor Function Test

MAL – Motor Activity Log; QOL includes SIS, SS-QOL, 5Q-5D

BDI – Beck Depression Inventory (assessed as both an efficacy and a safety measure)

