5.5 Handling of Missing Values and Outliers

All data collected under this protocol will be included in the assessment of safety. For AEs missing severity and relationship, if there is no other information available, relationship will be assessed as “possible” and severity will be assessed as “severe” for summary purposes, unless there is specific justification presented to impute other values. Missing or incomplete start dates will be imputed to the date of device implantation. Outliers that may have undue influence on the analysis and results will be discussed, but the results will not be based on any exclusion.

For the analysis of the efficacy endpoints, missing data will be imputed with a Last Observation Carried Forward approach. For any missing Visit 4 baseline data; the Visit 2 measure will be used as baseline. Multiple imputation, with missing at random assumptions using SAS PROC MI will also be performed as a sensitivity analysis. Data from the control group will be used to impute the missing in the VNS group. The specific imputation model will be defined prior to database lock. For the responder analysis, subjects with missing results will be imputed as non-responders for the initial evaluation, and a tipping point analysis will be used to assess sensitivity to missing data.

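### Every BDI safety measure in SAP 5.13.3 starts from Visit 4, after implant surgery, so none can show a subject's worsening already present by then

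*SAP*

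**What the plan says.** Section 5.13 lists three safety endpoints: adverse events, device complications and the BDI. Section 5.13.3 sets the BDI reference: "The change in the Beck Depression Inventory score from Visit 4 will be compared to each subsequent evaluation". The results are a change in total score, a change in depression category and a summary of the proportion worsening in each group.

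Section 3.3 places that visit: "The assessments after surgery, and before treatment (Visit 4) will be the baseline for statistical analyses". On the interval it says: "Subjects will start study therapy after an approximately one-week recovery period after surgery". It adds that the period may vary.

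Two other statements bear on what the safety analysis should cover. One of the primary objectives in section 2.1 is "safety of the surgical intervention and VNS stimulation". Section 5.13 says safety results will be given overall and by study phase, and the first phase is "study entry through surgery".

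The BDI or depression can also appear in two other outputs. Section 5.12 summarizes the BDI by group at each visit where it is collected, together with change from baseline. Section 5.13.1 tabulates adverse events by severity and by relatedness to device and to surgery.

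**The concern.** The safety objective names two exposures, the operation and the stimulation. Visit 4 separates them: it follows the first and precedes the second. As the reference for the stimulation question it is a good choice. When it is the only reference for a safety endpoint, any mood change between the pre-implant state and Visit 4 becomes part of the baseline.

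Two results follow for an individual subject. If a worsening around surgery persists, the subject is reported as unchanged. If it partly resolves, the subject is reported as improved while still worse than before implant. Both errors run in the reassuring direction. The control arm does not expose them, because all subjects in both arms are implanted (section 3).

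What is at stake is whether a named safety endpoint can say anything about the surgical half of the primary safety objective. No primary or secondary efficacy endpoint is touched.

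**Working it through.** The SAP states no BDI figure, so there is nothing to reproduce. The check sets the sections side by side and then uses one identity.

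**Sections side by side**

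| Point | Section | Content |
|---|---|---|
| BDI is a safety endpoint | 5.13 | Named as one of three |
| Reference visit | 5.13.3 | Visit 4, for score, category and proportion worsening |
| Timing of Visit 4 | 3.3 | After surgery, before therapy |
| Surgical safety | 2.1 | Part of a primary objective |
| Reporting phases | 5.13 | The first ends at surgery |
| Who is implanted | 3 | Both arms |

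A change that starts at Visit 4 cannot give a result for a phase that ends at surgery. No section specifies a comparison of a pre-implant BDI with Visit 4.

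**Identity.** For a later visit k:

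change from Visit 4 to k = (change from pre-implant to k) − (change from pre-implant to Visit 4)

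**Illustration.** Let s be an assumed rise in BDI between pre-implant and Visit 4, and r the share of it resolved by visit k, with nothing else changing. Then:

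- change from pre-implant = s(1 − r)
- change from Visit 4 = −s·r

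A positive value is a worsening. The values of s and r are assumptions, since the SAP gives no BDI data.

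| s | r | From pre-implant | From Visit 4 (as planned) |
|---|---|---|---|
| 2 | 0 | +2 | 0 |
| 2 | 0.5 | +1 | −1 |
| 2 | 1 | 0 | −2 |
| 4 | 0 | +4 | 0 |
| 4 | 0.5 | +2 | −2 |
| 4 | 1 | 0 | −4 |
| 6 | 0 | +6 | 0 |
| 6 | 0.5 | +3 | −3 |
| 6 | 1 | 0 | −6 |

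With no resolution the worsening disappears. With half resolved, the sign reverses.

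**One hypothetical subject.** BDI 8 before implant, 18 at Visit 4, 14 at Visit 7:

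- From Visit 4: 14 − 18 = −4, reported as improved.
- From pre-implant: 14 − 8 = +6, a worsening.

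**Between-arm comparison.** Let D be the expected change from pre-implant in each arm. If the expected shift s is common to both arms, then (D_VNS − s) − (D_control − s) = D_VNS − D_control. The shift cancels. A common shift is the natural expectation, because both arms are implanted and Visit 4 precedes therapy. The gap is therefore confined to within-subject change, which is the only place a peri-surgical BDI change could appear.

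**The case against.** The strongest case for the plan is that Visit 4 is a declared and consistent choice. The randomized contrast is stimulation against control stimulation, and Visit 4 isolates it. Section 2.1 does not assign surgical safety to the BDI in particular. A second reference would be an added analysis, not the correction of an error in an existing one. Much of this stands: Visit 4 should stay as the reference for stimulation, and worsening that first appears after Visit 4 is captured.

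A reader might also infer several stronger things that the SAP does not support:

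- **That mood worsening around surgery cannot be seen at all.** The by-visit summaries in 5.12 would show a group-level shift if the BDI is collected before implant, and 5.13.1 could show depression as a surgery-related adverse event. Neither closes the gap. Group summaries do not give subject-level worsening or category shifts, the change from baseline in 5.12 again runs from Visit 4 (by 3.3), and adverse events depend on investigator reporting.
- **That the proportion worsening is the only depression summary.** Section 5.13.3 also gives change in score and in category. They share the same reference.
- **That the safety baselines are mixed.** Section 5.5 says: "For any missing Visit 4 baseline data; the Visit 2 measure will be used as baseline". The paragraph opens by limiting itself to efficacy endpoints. Section 4.4 does give the BDI both an efficacy and a safety role, but nothing shows that the rule reaches 5.13.3.
- **That every implanted subject is misreported.** Only subjects whose BDI differs between the pre-implant assessment and Visit 4 would get a different result.
- **That Visit 4 should be replaced, and the earlier change called a surgical effect.** There is no unimplanted arm, so a pre-to-post change is uncontrolled and cannot be attributed to surgery alone.

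Finally, the SAP does not say that a pre-implant BDI exists. Section 3.3 mentions assessments before randomization without listing them, and the schedule may be in the protocol.

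**Conclusion.** The point holds in a limited form. As defined, the BDI measures in 5.13.3 cannot show subject-level worsening already present by Visit 4, and they can count a subject who is still worse than before implant as improved. This does not fit the surgical part of the primary safety objective or the first reporting phase in 5.13. The other outputs fill the gap only in part.

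The direction follows from the identity and needs no data. The size is unknown: the rises of 2, 4 and 6 points and the single-subject example are assumptions. The comparison of stimulation between arms is not biased. That statement assumes that the expected shift by Visit 4 is the same in both arms.

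The repair assumes that a BDI was recorded before implant. The change is worth making because it costs little and concerns a named safety endpoint, but it does not affect the trial's efficacy conclusions.

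**What to change.** In section 5.13.3:

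1. Keep Visit 4 as the reference for comparing stimulation with control.
2. Where a pre-implant BDI was recorded, name that visit and add change in score, change in category and proportion worsening from it:
   - to Visit 4, with arms pooled, descriptive only, and labelled as peri-surgical change and not as a surgical effect;
   - to each later visit, by group.
3. If no pre-implant BDI exists, state that the BDI cannot inform surgical safety and that this part of the objective rests on the other safety data.

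The cost is a few lines of SAP text and an extra column in an existing table. No further data collection is needed where the pre-implant value exists. The proportion worsening may look less favourable against the pre-implant reference.
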